7.8.5. Complete Remission Duration

CR duration is defined only for patients who achieve a CR during the study and is measured from the date of CR (Day 1) until relapse.

An additional rule for defining CR duration is:

 A patient found to have relapsed after missing one or more scheduled response assessments will have his CR duration end on the scheduled date for the first missed response assessment following the last confirmation of CR

Patients enrolled subsequent to protocol amendment 6 were scheduled to be followed for 2 years following the end-of-study visit, whereas patients enrolled prior to protocol amendment 6 were followed for only 30 days following the end-of-study visit unless they reconsented to the amendment-6, 2-year follow-up period. The definition of CR duration and the following rules for censoring CR duration apply to all patients regardless of follow-up duration.

Rules for censoring CR duration are:

- A patient who dies while in remission will have his CR duration censored on the date of death
- A patient in remission on the date he is lost to follow-up will have his CR duration censored on the date of his last response assessment
- A patient in remission on the database lock will have his CR duration censored on the date of his last response assessment

Summary statistics will include the number and percentage of patients who achieve a CR, the number and percentage of censored CR durations, quartile CR durations, 95% CIs for the quartile CR durations, and KM "survival" percentages with 95% CIs at select milestone times (e.g., 6, 12 and 18 months).

Two endpoints analogous to CR duration will be analyzed using similar methods.

- Combined CR Duration (defined only for patients who achieve a combined CR during the study): time from the earliest date of combined CR (Day 1) until relapse after combined CR
- Combined Remission Duration (defined only for patients who achieve combined remission during the study): time from the earliest date of combined remission (Day 1) until relapse after combined remission

Response categories included in "combined CR" and "combined remission" are delineated in Section 3.

7.8.6. ECOG Performance Status

ECOG performance status will be summarized within and across alvocidib dose levels using shift tables.

7.9. Biomarker

The biomarker in this study is MCL-1 dependence measured by mitochondrial sensitivity to NOXA BH3 peptides. Relevant data supporting analyses of MCL-1 dependence will be listed by patient within alvocidib dose level. Summary of baseline biomarker values will include descriptive statistics appropriate for continuous variables (see section 7.6). An LR model will be fit to examine the relationship between baseline MCL-1 dependence and the independent binary variable CR for newly diagnosed AML patients receiving ACM. In addition, area under the curve (AUC) will be calculated (by treatment

arm) for the trapezoidal receiver operating characteristic (ROC) curve. This value will quantify the ability of MCL-1 dependence to predict CR.¹¹ Ninety-five percent Cls will be calculated by assuming estimated AUC follows a normal distribution.

$$\widehat{AUC} \pm z_{1-\alpha/2} SE_{AUC}$$

where the standard error SE_{AUC} is calculated by the jackknife method.¹² Similar analyses will be conducted for combined CR and combined remission.

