11.3.3 Biomarker Prediction Endpoint Analyses

Summary of baseline biomarker values will include within- and between-treatment-arm descriptive statistics. If there are sufficient numbers of patients achieving remissions for an analysis to be informative, a logistic regression model will be fit to examine the relationship between baseline results and other potential biomarkers (including, but not limited to, MCL-1 dependency) and the independent binary variables complete remissions and overall remissions during the study. In addition, area under the curve (AUC) and 95% CI will be calculated (by alvocidib dose level) for the trapezoidal receiver operating characteristic curve. This value will quantify the ability of certain biomarkers (including, but not limited to, MCL-1 dependency) to predict complete/overall remissions.

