4.2. Statistical Objectives

The statistical objectives are threefold:

- 1. To define a maximum tolerated dose of alvocidib administered with cytarabine and daunorubicin in newly diagnosed AML patients
- 2. To describe the safety and efficacy of alvocidib administered with cytarabine and daunorubicin in newly diagnosed AML patients

3. To model the relationship between baseline MCL-1 dependence and response to treatment with alvocidib administered with cytarabine and daunorubicin

5. Sample Size

The sample size for this study is not predetermined. The number of patients enrolled depends on the occurrence and pattern of DLTs.

6. Treatment Assignment

Cohorts of 3 patients are assigned a dose of alvocidib according to standard 3+3 dose escalation/de-escalation rules. All patients receive the same, standard doses of cytarabine and daunorubicin.

7. Statistical Methods

Analyses will be performed using SAS statistical software. Default estimation methods in version 9.4 of SAS are always used unless an alternative is specified below. Data summaries will include the mean, standard deviation, median, minimum and maximum values for continuous data; the median, 25th and 75th percentiles, minimum and maximum values for time-to-event endpoints; and the number and percentage of patients in each category for categorical data. Pointwise 95% confidence intervals (CI) will also be estimated for the mean (continuous data), median (time-to-event endpoints) or percentage of patients (categorical data).

In general, data values will be obtained directly from the clinical database (e.g., birth date, treatment dates, AML relapse date and death date). Derivations for certain values not collected explicitly in the database are explained in relevant sections below (e.g., age and treatment failure date, sections 7.6 and 7.8.2, respectively). In some instances, it is beyond the scope of this SAP to explain schemes for patient classifications and data derivations (e.g., classifying patients in cytogenetic risk group according to published criteria). These details will be expounded in the clinical study report.

Durations of time expressed in months (e.g., times-to-event endpoints) will be reported in proportional "months" according to the formula

months =
$$\frac{12}{365.25} \times \text{days}$$

Baseline value of a characteristic is defined as the last measured value prior to the first dose of study drug.

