Appendix 2. Sample Table Template

Tolero Pharmaceuticals ALV-101

Patient Disposition (Intent-to-Treat Population) Table X.X

Page 1 of 327

	Alvocidib $20/30 \text{ mg/m}^2$ $(N=3)$	Alvocidib $30/40 \text{ mg/m}^2$ (N=3)	Alvocidib $30/50 \text{ mg/m}^2$ $(N=3)$	Alvocidib $30/60 \text{ mg/m}^2$ $(N=13)$	Study Total (N=22)
Study Center Columbia University Medical Center University of North Carolina Johns Hopkins University	3 (100%)	1 (33.3%) 2 (66.7%) 0	3 (100%) 0	2 (15.4%) 7 (53.8%) 4 (30.8%)	6 (27.3%) 12 (54.5%) 4 (18.2%)
Country United States	3 (100%)	3 (100%)	3 (100%)	13 (100%)	22 (100%)
Protocol Version Amendment 2 Amendment 3 Amendment 4	1 (33.3%) 2 (66.7%) 0	3 (100%) 0	3 (100%) 0	0 0 13 (100%)	1 (4.5%) 8 (36.4%) 13 (59.1%)
Safety Analysis Population Yes	3 (100%)	3 (100%)	3 (100%)	13 (100%)	22 (100%)
Response Evaluated Analysis Population Yes	3 (100%)	3 (100%)	3 (100%)	13 (100%)	22 (100%)
Alvocidib and 7+3 Induction Yes	3 (100%)	3 (100%)	3 (100%)	13 (100%)	22 (100%)

[[]a] Number of weeks from the first dose of alvocidib to withdrawal from study

Source: Data Extract ddmmmyy; SAS (v9.4) ddmmmyy at hh:mm

Statistical Analysis Plan Protocol TPI-ALV-201

Tolero Pharmaceuticals ALV-101	ticals ALV-101	Table X.X Patient Disposition (Intent-to-Treat Population)	X.X sposition t Population)				Page 2 of 327
		Alvocidib 20/30 mg/m² (N=3)	Alvocidib 30/40 mg/m² (N=3)	Alvocidib 30/50 mg/m² (N=3)	Alvocidib 30/60 mg/m² (N=13)	Study Total (N=22)	
	Alvocidib and 5+2 Reinduction Yes No	3 (100%)	1 (33.3%) 2 (66.7%)	3 (100%)	1 (7.7%) 12 (92.3%)	2 (9.1%) 20 (90.9%)	
	HiDAC Consolidation Cycles 0 1 2 3 4	1 (33.3%) 1 (33.3%) 0 1 (33.3%)	2 (66.7%) 0 0 0 0 1 (33.3%)	1 (33.3%) 0 1 (33.3%) 1 (33.3%) 0 1 (33.3%)	9 (69.2%) 3 (23.1%) 1 (7.7%) 0	13 (59.1%) 4 (18.2%) 2 (9.1%) 2 (9.1%) 1 (4.5%)	
	Weeks on Study ^[a] Mean (S.D.) Median Min, Max	19.7 (13.8) 17.7 7.0, 34.4	15.0 (11.0) 9.4 7.9, 27.6	15.0 (8.1) 14.4 7.3, 23.4	8.1 (3.6) 9.0 3.9, 12.3	13.6 (9.1) 10.0 3.9, 34.4	
	Primary Reason Patient was Withdrawn from the Study Completed the Study Death Relapsed Disease (following remission) Lack of Efficacy (failure to achieve remission) Unknown Missing	2 (66.7%) 0 0 0 0 1 (33.3%)	2 (66.7%) 0 0 1 (33.3%) 0	1 (33.3%) 0 1 (33.3%) 1 (33.3%) 0 0	2 (15.4%) 1 (7.7%) 1 (7.7%) 1 (7.7%) 0 8 (61.5%)	7 (31.8%) 1 (4.5%) 2 (9.1%) 3 (13.6%) 1 (4.5%) 8 (36.4%)	

[a] Number of weeks from the first dose of alvocidib to withdrawal from study

Source: Data Extract ddmmmyy; SAS (v9.4) ddmmmyy at hh:mm

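### The planned biomarker AUC interval cannot exist in a 3-patient dose level, and when patients are pooled it under-covers, mainly at small N or high AUC

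*SAP*

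**What the plan says.** Protocol 11.3.3: "area under the curve (AUC) and 95% CI will be calculated (by alvocidib dose level) for the trapezoidal receiver operating characteristic curve". The sentence before it makes the logistic model conditional on there being enough remissions. The AUC sentence carries no such condition.

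SAP 7.9 sets a different grouping: "area under the curve (AUC) will be calculated (by treatment" arm). It then fixes the method. The 95% limits "will be calculated by assuming estimated AUC follows a normal distribution", that is, the estimate plus or minus z times its standard error, and that standard error "is calculated by the jackknife method". The SAP adds: "Similar analyses will be conducted for combined CR and combined remission".

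SAP section 6 gives the group sizes: "Cohorts of 3 patients are assigned a dose of alvocidib according to standard 3+3 dose escalation/de-escalation rules". Protocol Table 3 allows 3 to 6 patients per level. The sample table in SAP Appendix 2 shows levels of 3, 3, 3 and 13, in total 22.

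Neither document sets a minimum number of responders and non-responders for the AUC, a fallback when it is undefined, or a bounded interval. Neither says outright that a pooled AUC will be calculated.

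**The concern.** An AUC compares every responder with every non-responder, so it needs both kinds of patient. A delete-one jackknife needs both kinds to remain after any single patient is removed. Cohorts of 3 cannot meet that. Read by dose level, the plan asks for an interval that its own method cannot produce in most levels.

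Reading arm as all patients together restores the calculation but leaves a second difficulty. A symmetric normal interval takes no account of the upper bound of 1 and behaves poorly in small samples when the AUC is high.

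Relating MCL-1 dependence to response is the third statistical objective in SAP 4.2, and the AUC is the planned measure of predictive ability. An interval with less than its nominal coverage, or one that collapses to a single point, would overstate what the study shows about the marker.

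**Working it through.** **Inputs from the documents.** Two-sided 95%, z = 1.96. Dose levels of 3 to 6 (Protocol Table 3). Appendix 2 template: 3 + 3 + 3 + 13 = 22. Protocol 11.2: up to 40 patients; its scenario is 3 + 3 + 6 + 3 + 20 = 35, with 6 + 20 = 26 at the MTD. CR rates of 46% and 70% are the two arms of the earlier randomised study in Protocol 2.6.2.

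**Assumptions not in the documents.** Those CR rates carried over to this trial, a CR rate of 65% for pooled patients, a continuous binormal marker, and true AUC 0.5 to 0.9.

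**1. When the jackknife exists.** With m responders and k non-responders, AUC = (number of concordant pairs)/(m·k), and SE = √[((n−1)/n)·Σ(AUC₍₋ᵢ₎ − mean)²]. Every leave-one-out AUC must be defined, so m ≥ 2 and k ≥ 2, hence n ≥ 4.

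- n = 3, split 3/0 or 0/3: no AUC.
- n = 3, split 2/1 or 1/2: the AUC exists, but deleting the lone patient makes m·k = 0, so there is no SE.

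The probability of a CI at n = 3 is therefore 0 at any CR rate. The point estimate exists with probability 1 − p³ − (1−p)³:

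- p = 0.46: 1 − 0.097 − 0.157 = 0.745
- p = 0.70: 1 − 0.343 − 0.027 = 0.63

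**2. Six patients.** P(no CI) = P(X ≤ 1) + P(X ≥ 5), with X binomial:

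- p = 0.46: 0.025 + 0.127 + 0.067 + 0.009 = 0.228
- p = 0.70: 0.001 + 0.010 + 0.303 + 0.118 = 0.431 (rounded terms)

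At n = 13 the CI is computable with probability 0.995 and 0.94 respectively. At n = 26 the probability is above 0.998.

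**3. Pooled patients.** Simulated performance of the nominal 95% jackknife interval, CR 65% unless marked:

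| True AUC | Coverage, N=22 | Upper limit >1, N=22 | Coverage, N=40 | Upper limit >1, N=40 |
|---|---|---|---|---|
| 0.5 | 92% | 5% | 94% | under 2% |
| 0.7 | 90–91% | 33% | 93% | under 2% |
| 0.8 | 88% | 64% | 92% | 7–19%* |
| 0.9 | 82% | 88% | 88% | 53–66%* |

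*Range over CR 46% to 70%. At CR 70%, the N=40, AUC 0.7 figure is 4%.

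**4. Perfect separation.** If every responder scores above every non-responder, all leave-one-out AUCs equal 1, the SE is 0 and the interval is [1, 1]. This happens in 4% to 7% of data sets at N=22 with true AUC 0.9.

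**5. A bounded alternative.** The Newcombe score-type limits solve |AUC − θ| = z√V(θ), with V(θ) = θ(1−θ)[1 + N*(1−θ)/(2−θ) + N*θ/(1+θ)]/(mk) and N* = (m+k)/2 − 1. Coverage is 95% to 97% in the settings above. For an observed AUC of 1 with m = 14 and k = 8 (mk = 112, N* = 10), the lower limit solves 1 − θ = (3.84/112)·θ·[…]. At θ = 0.804 the bracket is 7.10, and both sides are 0.196. The interval is about [0.80, 1], where the jackknife gives [1, 1].

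**6. Average width, jackknife against score-type (CR 65%).** N=22: 0.57 v 0.45 (AUC 0.5), 0.50 v 0.42 (0.7), 0.41 v 0.38 (0.8), 0.27 v 0.32 (0.9). N=40: 0.36 v 0.32 (0.7).

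**The case against.** The strongest reply is that the SAP does not clearly ask for a jackknife by dose level. The dose-level grouping is in the Protocol and the jackknife is in the SAP. Protocol section 11 calls itself an overview and leaves full detail to the SAP. The SAP names dose levels when it means them, and its MCL-1 deciles in 7.8.1 ignore arm, so one pooled AUC is a natural reading. That is fair, and it makes the wording ambiguous rather than plainly wrong. It does not remove the need to reconcile the two documents, and the pooled interval still under-covers.

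A reader might infer more than the documents support:

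- *That no AUC can be computed at n = 3.* The point estimate exists in 2/1 and 1/2 splits. Only the SE and CI fail.
- *That the planned interval is simply too narrow.* On average it is wider than the score-type interval for true AUC 0.5 to 0.8. The shortfall comes mainly from its shape: the SE shrinks as the estimate nears 1, and part of its length lies above 1.
- *That it generally runs past 1.* This is common at N=22 with a high AUC and rare at N=40 with AUC at most 0.7.
- *That a main objective fails.* SAP objective 3 is to model the relationship, which the logistic model does. The AUC is additional, and Protocol section 3 lists biomarkers as exploratory.

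It also stands that the expansion level will usually yield an interval.

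**Conclusion.** The point holds in limited form. That no jackknife CI exists in any 3-patient dose level is exact and needs no assumption about the marker or the CR rate. On the Appendix 2 sizes it applies to three of the four levels. The 23% to 43% failure rate at n = 6 depends on the borrowed CR rates.

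The pooled under-coverage rests on an assumed true AUC, CR rate and binormal marker. It is 3 to 13 points at N=22 and 1 to 7 points at N=40 over AUC 0.5 to 0.9. At N=40 with an uninformative or weak marker the planned interval is nearly adequate.

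Severity is minor to moderate: the analysis is exploratory and no dose decision uses it, but the plan leaves the analyst without a workable rule.

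**What to change.** Amend SAP 7.9 and clarify Protocol 11.3.3 so that both say the same:

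1. Estimate one AUC over all patients with baseline MCL-1 data for each of CR, combined CR and combined remission, in place of by arm or by dose level.
2. Report a CI only when there are at least 2 responders and 2 non-responders; otherwise give the counts and say that no interval is estimable. This matters most for combined CR and combined remission, where non-responders are fewer.
3. Replace the jackknife normal interval with a range-preserving one. The Newcombe score-type interval is one suitable choice among several.

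The cost is wording only; no new data are needed. By-dose AUCs are lost, but in 3-patient levels they carry no usable information. The new interval is not a general loss of precision: it is narrower on average for AUC up to 0.8 and wider only near 0.9.

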7.10. Safety Endpoints

Summaries of safety endpoints will include data collected from the safety patient population. Relevant data supporting safety analyses will be listed by patient within alvocidib dose level.

7.10.1. 30- and 60-Day Mortality

Estimates of 30- and 60-day mortality and their pointwise 95% CIs will be derived from KM curves for OS by treatment arm (see section 7.8.3).

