2.6.2.3 Summary of Safety in NCI-8972 (J-1101) FLAM in Newly-diagnosed Poor-risk AML

In this comparison of FLAM vs. 7+3, adverse events were similar in both arms. Comparative adverse events Grade ≥ 3 included (FLAM, 7+3): febrile neutropenia (48%, 45%), infection (35%, 38%), hepatic dysfunction (21%, 23%), and GI events (11%, 9%).

Based on previous observations of Tumor Lysis Syndrome in prior AML studies of FLAM, preventive measures were included in this study including the use of allopurinol, phosphate binder, hydration, and rasburicase was allowed per institutional policy for hyperuricemia. The rates of TLS were similar between FLAM and 7+3 (FLAM: 8% versus 7+3: 7%). Treatment-related mortality was also similar between the arms at 30 days: FLAM: 5% versus 7+3: 2%, or at 60 days FLAM: 10% versus 7+3: 4%. The majority of early deaths (8/11 patients) on FLAM were >60 years.

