11.2 Sample Size

Given the design and primary objectives of this study, the sample size will be determined by the guidelines governing dose escalation/de-escalation and the identification of DLTs. As a result, the final sample size is not fixed and will not be determined by consideration of inferential analyses conducted via statistical hypothesis testing. It may be anticipated that the study sample size will be up to 40 patients. This is based on observing DLTs in 2 of 3 patients enrolled at the fourth dose level (Cohort 4) and declaring the third dose level as the MTD (3 patients each in the first and second dose levels, 6 patients in the third dose level during dose escalation, 3 patients at the fourth dose level, and an additional 20 patients at the third dose level for confirmation of safety as well as additional safety analysis and feasibility for determining MRD by dual methods [ie, MPFC and NGS] at a central laboratory). However, the actual number of patient enrolled may be slightly more or less depending on the actual pattern and frequency of DLTs.

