30- and 60-day survival, adverse events, time to neutrophil recovery, time to platelet recovery, prevalence of tumor lysis syndrome, clinical laboratory parameters, vital signs

Statistical Methods:

Descriptive statistics (including 95% confidence intervals) within and across alvocidib dose levels

2. Abbreviations

Standard abbreviations (e.g., AML = acute myeloid leukemia and mg = milligrams) are omitted intentionally.

AE Adverse Event

AML Acute Myeloid Leukemia
ANC Absolute Neutrophil Count

ATC Anatomical and Therapeutic Class

AUC Area Under Curve

BM Bone Marrow

BSA Body Surface Area
Cl Confidence Interval

CM Ara-C (Cytarabine) and Mitoxantrone

CMH Cochran-Mantel-Haenszel (test)

CR Complete Remission

CRi Complete Remission with Incomplete Blood Count Recovery

CTCAE Common Terminology Criteria for Adverse Events

DDE Drug Dictionary Enhanced

DLT Dose-Limiting Toxicity

DSMB (Independent) Data Safety Monitoring Board

ECOG Eastern Cooperative Oncology Group (performance status)

ELN European LeukemiaNet

HiDAC High-Dose Cytarabine

HR Hazards Ratio

ITT Intent-to-Treat (patient population)

IWG International Working Group

KM Kaplan-Meier (survivor function estimate)

LR Logistic Regression

MedDRA Medical Dictionary for Regulatory Activities

MRD- Minimal Residual Disease Negative

MTD Maximum Tolerated Dose

OS Overall Survival

PBSC Peripheral Blood Stem Cells
PFS Progression-Free Survival

PH Proportional Hazards (model)

PR Partial Remission

PT (MedDRA) Preferred Term

RFS Relapse-Free Survival

ROC Receiver Operating Characteristic (curve)

SAE Serious Adverse Event SAP Statistical Analysis Plan

SCT Stem Cell Transplant/Transplantation

SMQ Standardized MedDRA Query

SOC (MedDRA) System Organ Class

TEAE Treatment Emergent Adverse Event

TLS Tumor Lysis Syndrome

WHO World Health Organization

3. Definitions

Standard statistical terminology (e.g., type-1 error rate and significance level) is omitted intentionally. Efficacy endpoints are defined in Section 4.1 below (see Table 1).

Baseline Value: last measured value prior to the first dose of study drug

Combined CR: response assessment of CR or CRi

Combined Remission: response assessment of CR, CRi or PR

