7.8.1. Remission Rates

The primary efficacy endpoint is CR rate as assessed by the investigator following treatment with alvocidib. Patients who, for any reason, do not supply bone marrow for response assessment are counted among those not achieving remission.

Summary statistics will include the number and percentage of patients rated as not achieving CR due to not providing a bone marrow biopsy/aspirate, proportion of patients who achieve a CR and exact 95% CI estimated without stratification. Between—treatment-arm statistics will include the Mantel-Haenszel odds ratio and 95% CI estimated with stratification.

A standard logistic regression (LR) model will be estimated relating the probability of achieving CR as a function of baseline MCL-1 dependence. Results will be presented graphically as follows. Patients will be divided into groups according to which range of values their baseline MCL-1 dependence falls:

$$(0\%-\leq d_1), (d_1-\leq d_2), (d_2-\leq d_3), \dots, (d_8-\leq d_9), (d_9-100\%)$$

where $d_1,...,d_9$ are deciles for baseline MCL-1 dependence regardless of treatment arm. Empirical CR rates will be calculated for patients within each range and plotted alongside CR probabilities estimated from the LR model.

Other remission rates (e.g., combined CR rate and combined remission rate) will be summarized similar to CR rate.

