7.8.3. Overall Survival

OS time is defined for all patients and is measured from the date of first dose (Day 1) until death from any cause. Patients enrolled subsequent to protocol amendment 6 were scheduled to be followed for 2 years following the end-of-study visit, whereas patients enrolled prior to protocol amendment 6 were followed for only 30 days following the end-of-study visit unless they reconsented to the amendment-6, 2-year follow-up period. The definition of OS time and the following rules for censoring OS time apply to all patients regardless of follow-up duration.

Rules for censoring OS time are:

- A patient with OS continuing as of the date he is lost to follow-up will have his OS time censored on the date of his last assessment of any type
- A patient with OS continuing as of the database lock will have his OS time censored on the date of his last assessment of any type

Summary statistics will include the number and percentage of censored OS times, quartile OS times, 95% CIs for the quartile OS times, and KM survival percentages with 95% CIs at select milestone times (e.g., 6, 12 and 18 months).

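### The 30- and 60-day mortality intervals give no upper limit for any dose level without a death by the landmark, the likely outcome in levels of 3 to 6 patients

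*SAP*

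**What the plan says.** SAP Table 1 lists 30- and 60-day mortality as a safety endpoint. SAP 7.10.1 gives the method in one sentence: "Estimates of 30- and 60-day mortality and their pointwise 95% CIs will be derived from KM curves for OS by treatment arm". It points to SAP 7.8.3, where the overall survival output includes "KM survival percentages with 95% CIs at select milestone times (e.g., 6, 12 and 18 months". Neither section names a form of interval or says what to report when nobody has died.

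SAP section 7 fills such gaps with a general rule: "Default estimation methods in version 9.4 of SAS are always used unless an alternative is specified below". The SAP synopsis adds the reporting level: "Descriptive statistics (including 95% confidence intervals) within and across alvocidib dose levels".

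The groups are small. SAP section 6 states: "Cohorts of 3 patients are assigned a dose of alvocidib according to standard 3+3 dose escalation/de-escalation rules". The planning scenario in Protocol 11.2 has "3 patients each in the first and second dose levels, 6 patients in the third dose level during dose escalation, 3 patients at the fourth" level, plus 20 more patients at the third level, taken as the maximum tolerated dose (MTD). Protocol 11.3.2 says only that all-cause mortality at 30 and 60 days will be calculated.

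For the complete remission rate, also a proportion in the same small groups, SAP 7.8.1 asks for an "exact 95% CI estimated without stratification".

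**The concern.** A Kaplan-Meier interval takes its width from the observed deaths. If there are none before the landmark, the method has nothing from which to estimate uncertainty, whatever the group size. A level with 0 deaths among 3 patients and one with 0 among 26 would get the same result, although the second is far stronger evidence.

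Safety and tolerability are the trial's primary objective, and early death is the gravest safety outcome that it tabulates. In a small group without deaths, what the reader needs is the highest mortality still compatible with the data. The planned method leaves that figure out, and it does so where information is scarcest.

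**Working it through.** The documents give no figure for this interval, so there is nothing to reproduce. The check has three steps.

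**Inputs**
- Group sizes: 3 and 6 (3+3 design); 6 + 20 = 26 at the MTD (Protocol 11.2).
- Day 60 mortality: 8% from any cause in the two-schedule alvocidib study (Protocol 2.6.2.2; 3/39 = 7.7% per arm) and 10% treatment-related on alvocidib in the randomized comparison with 7+3 (Protocol 2.6.2.3). Protocol 2.6.2.1 lies between them: 2 + 2 = 4 treatment-related deaths among 45 patients, or 8.9%.
- Day 30 mortality: 5% on alvocidib (Protocol 2.6.2.3).
- Low end: 2%, the 30-day figure for 7+3 without alvocidib (Protocol 2.6.2.3).

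These rates come from other regimens, and some count only treatment-related deaths. Using them for this trial is an assumption.

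**Step 1: the interval with no deaths.** Greenwood: Var(S) = S² × G, with G = Σ d/[n(n − d)] over the death times. With no deaths the sum is empty, so S = 1 and G = 0.
- Linear: S ± 1.96 × S√G = 1 ± 0. Mortality is 0% (0%, 0%).
- Log: S × exp(±1.96√G) = 1 × exp(0) = 1. Mortality is 0% (0%, 0%).
- Log-log: S^exp(±1.96√G/|ln S|). Here √G/|ln S| = 0/0, so the interval is undefined.

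The documents do not say which form applies, but none of the three gives an upper limit. With one death the log-log form works: mortality 5.5-94.6% at n = 3, 2.5-72.7% at n = 6 and 0.6-24.3% at n = 26.

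**Step 2: how often a level has no deaths.** P(no death) = (1 − p)^n, with complete follow-up:

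| True mortality | n = 3 | n = 6 | n = 26 |
|---|---|---|---|
| 2% | 94% | 89% | 59% |
| 5% | 86% | 74% | 26% |
| 8% | 78% | 61% | 11% |
| 10% | 73% | 53% | 7% |

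For example, 0.92³ = 0.779, 0.90⁶ = 0.531 and 0.95²⁶ = 0.264. The Protocol 11.2 scenario has final levels of 3, 3, 26 and 3. If all four share the same mortality, the expected number without a death by Day 60 is 3 × 0.779 + 0.114 = 2.45 at 8%, and 3 × 0.729 + 0.065 = 2.25 at 10%.

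**Step 3: what an exact interval would show.** The Clopper-Pearson upper limit with no deaths is 1 − 0.025^(1/n):
- n = 3: 70.8%
- n = 6: 45.9%
- n = 26: 13.2%

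**The case against.** **The failure is narrow.** It needs a group with no deaths by the landmark, or one in which everybody has died. A reader might infer that the Kaplan-Meier interval is poor throughout, because its log-log coverage at 5% mortality and n = 26 is only 70%. That figure scores every missing interval as a miss, so it mostly restates the 26% chance of no deaths. Given at least one death, coverage there is 95%. This objection stands, and the point is confined to groups without deaths.

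**A blank is not a claim of certainty.** A reader might also infer that early mortality will always look exactly known. That fits only the zero-width forms. Under the log-log form nothing is printed. The documents do not name the form, so they support only the statement that no upper limit is reported.

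**Little depends on it.** The analysis is descriptive. Escalation and the MTD rest on dose-limiting toxicities, which include most Grade 5 events (Protocol 4.4.3). The tables show group sizes, and SAP 7.10.2 counts adverse events leading to death. This limits the seriousness of the point. It does not supply the missing limit, and the adverse event count covers a different window. A patient whose last dose is on Day 11 leaves the treatment-emergent period after Day 41 (11 + 30).

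**The pooled row would usually work.** With 3 + 3 + 6 + 3 + 20 = 35 patients, the chance of no deaths is 17% at 5% mortality and 2.5% at 10%. This is true, but SAP 7.10.1 itself asks only for results by arm, and pooled mortality does not describe a single dose level.

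**Kaplan-Meier handles censoring.** Under SAP 7.8.3, patients can be censored before Day 60, and some were followed for only 30 days after the end-of-study visit. Plain deaths/n would count them as survivors. This stands, and the fix allows for it.

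**Conclusion.** The point holds for groups without a death by the landmark. There the planned 95% interval has zero width or is undefined, and no upper limit on mortality is given. This follows from algebra and needs no assumed rate.

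How often it happens does depend on assumed rates. At the 60-day alvocidib figures of 8-10%, most levels of 3 or 6 patients would have no deaths, while a 26-patient MTD level would usually have at least one. The 5% row suits the Day 30 landmark, since the protocol reports that rate at 30 days. As a 60-day rate it would overstate the frequency.

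The documents do not support a wider criticism of Kaplan-Meier estimation here, or any effect on dose escalation. This is a reporting gap in a named safety endpoint. It should be corrected, but it does not threaten the conduct of the trial.

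**What to change.** Amend SAP 7.10.1 as follows:
- Replace the reference to treatment arm with dose level and overall.
- Where vital status at the landmark is known for every patient in the group, report deaths/n by Day 30 and by Day 60 with exact (Clopper-Pearson) 95% limits.
- Where any patient is censored before the landmark, keep the Kaplan-Meier estimate and use an interval that remains valid with zero events. Beta-product limits are one choice; without censoring they equal Clopper-Pearson.
- State how many patients in each group were censored before each landmark.

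Kaplan-Meier curves may remain as supportive output. The change brings the endpoint into line with the exact limits already planned for the complete remission rate.

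The cost is a few sentences in the SAP, minor programming (availability of beta-product limits in the planned software should be confirmed) and wider intervals. No new type of data is needed, although the exact limits depend on establishing vital status at Day 30 and Day 60.
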